The primary safety endpoints will be the incidence of pre-defined complications related to local anesthetic systemic toxicity (exceedingly rare in all phase 2 and 3 trials), and the percentage of families properly disposing of leftover opiate medication at 10-14 days postoperatively.

The primary analysis will involve two separate comparisons: 1) Comparison of primary efficacy endpoints between those receiving Exparel® plus 0.25% Bupivacaine versus those receiving standard 0.25% Bupivacaine alone, and 2) Comparison of primary safety endpoints between those receiving Exparel® plus 0.25% Bupivacaine versus those receiving standard 0.25% Bupivacaine alone.

- b. Secondary outcome variables.

Date: 12/1/2021

Principal Investigator: [name] [name]

Application Number: IRB00284462

ClinicalTrial.gov Identifier: NCT04826484

Secondary outcomes will include a cost comparison of Exparel® plus 0.25% Bupivacaine versus standard 0.25% Bupivacaine alone, as well as evaluating efficacy of using Exparel® for a penile nerve block versus incisional infiltration with regard to safety and efficacy.

c. Statistical plan including sample size justification and interim data analysis.

All patients that meet inclusion criteria for the trial and are consented will undergo cross-randomization (Figure 1) to receive either 0.25% Bupivacaine or Exparel® plus 0.25% Bupivacaine, opioid medication instructions with disposal instructions, or opioid medication instructions without disposal instructions.

Currently at Johns Hopkins, we perform over 500 minor pediatric urologic procedures per year, roughly 20% of which involve patients 6 years or older and could be eligible for inclusion.

We assumed that the smallest detectable difference in the primary endpoints may be the percentage of patients who are opiate-free at 48 hours and thus planned to base our power calculation on detecting a difference in this variable. Prior studies from our institution have demonstrated that roughly 28% of pediatric patients undergoing minor urologic procedures and receiving standard Bupivacaine local wound infiltration require zero opioids postoperatively.² This study will be conducted with a superiority design (does penile block or wound infiltration with Exparel® plus 0.25% Bupivacaine offer a superior opiate-free rate at 48 hours than standard Bupivacaine?).

Power of 80% (beta = 0.2) and two-sided alpha of 0.05 for increasing opiate-free rate

28% to 60%: n = 74; 37 in each arm

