28% to 50%: n = 152; 76 in each arm

28% to 40%: n = 486; 243 in each arm

28% of peds uro pts from recent JHH anesthesia study required zero opiates

Consensus among the study investigators suggested that a 50% opioid-free rate at 48 hours (22% absolute difference between arms) would be the minimal clinically relevant difference in the primary outcome measure.

Assuming a 25% rate of lost-to-follow-up or incomplete follow-up data, we will plan to enroll 100 pediatric patients per arm, or 200 patients total. Target enrollment may be subject to change if the lost to follow-up rate is significantly higher or lower than 25%.

Randomization lists will be generated by the study coordinator. The investigators will maintain the randomization list, password protected, on a remote drive maintained by the Department of Urology and will provide the random assignment to the study coordinator as each patient is enrolled.

One interim analysis of the primary efficacy and primary safety endpoint will be planned with potential early stopping for efficacy or futility. The interim analysis will be conducted after half

Date: 12/1/2021

Principal Investigator: [name] [name]

Application Number: IRB00284462

ClinicalTrial.gov Identifier: NCT04826484

of the patients have been enrolled. O'Brien-Fleming boundaries will be used, as implemented in PASS v. 11 (NCSS Software, Inc., Kaysville, UT).

One interim analysis of the primary efficacy endpoint will be conducted after information proportion of 0.66 (n = 102) to assess for early stopping for efficacy or futility. The total sample size needed for 80% power with a 1-sided test was 152 patients (76 per arm), based on 10,000 simulations. Alpha-spending at the interim analysis and final analysis was 0.016 and 0.034 (cumulative alpha spent 0.016, 0.05), respectively. The futility boundaries at the interim analysis and final analysis were p=0.24 and p=0.048, respectively. At the interim analysis the rates of all-cause surgical complications and those attributable to sequela of the local anesthetics or symptoms related to LAST were also evaluated. An unacceptable rate of all-cause surgical complications was >10%. If the lower 95% confidence bounds met or exceeded this rate for all-cause complications or there were any episodes of LAST, the trial would have been halted for further review and consideration of early stopping.

Statistical Analysis

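### Section 7c justifies the same 152 patients under two-sided alpha 0.05 and under a 1-sided group-sequential test with alpha 0.05, so the success rule for the primary comparison is undefined

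*Combined protocol and SAP*

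**What the plan says.** All of this is current text in section 7c of the combined protocol and SAP.

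- **Sample-size paragraph.** The basis is "Power of 80% (beta = 0.2) and two-sided alpha of 0.05 for increasing opiate-free rate". Three scenarios follow: "28% to 60%: n = 74; 37 in each arm", "28% to 50%: n = 152; 76 in each arm" and "28% to 40%: n = 486; 243 in each arm". The investigators choose 28% to 50%. No interim look is mentioned here.
- **Second interim paragraph.** It places one interim at information 0.66 (n = 102) and states "The total sample size needed for 80% power with a 1-sided test was 152 patients (76 per arm), based on 10,000 simulations". It adds: "Alpha-spending at the interim analysis and final analysis was 0.016 and 0.034 (cumulative alpha spent 0.016, 0.05), respectively". And: "The futility boundaries at the interim analysis and final analysis were p=0.24 and p=0.048, respectively". No final p-value limit is labelled as the efficacy limit.
- **Statistical Analysis.** The 48-hour opioid-free rate is compared by chi-squared test. Neither sidedness nor a significance threshold is given. If adjustment is needed, logistic regression gives an odds ratio with a 95% confidence interval.
- **Section 7d.** The trial is to stop if futility is met at the interim.

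The first interim paragraph times the look differently: "The interim analysis will be conducted after half" of the patients are enrolled.

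**The concern.** The two statements give the same sample size and the same power for different tests. A two-sided 0.05 test allows a 2.5% chance of falsely declaring benefit. A 1-sided test with cumulative alpha 0.05 allows 5%. A design that needs 152 patients for 80% power under the first should need fewer under the second, even after paying for one O'Brien-Fleming-type look.

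What is at stake is the verdict on the comparison that the trial is powered for. If sidedness stays open until the data are in, the same result can be reported as positive or negative.

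**Working it through.** **Inputs (section 7c):** control 28%, target 50%, 1:1 allocation, 80% power; interim at information 0.66 (n = 102, so 51 per arm; 102/152 = 0.671), final at 76 per arm; spends 0.016 and 0.034; futility boundaries 0.24 and 0.048.

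**1. The two-sided sizing reproduces.** The pooled formula per arm, without continuity correction, is

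n = [z_α √(2p̄q̄) + z_β √(p₁q₁ + p₂q₂)]² / (p₂ − p₁)².

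For 28% vs 50%, p̄ = 0.39:

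- Two-sided 0.05: [1.960 × 0.6898 + 0.8416 × 0.6720]² / 0.22² = 3.677/0.0484 = 75.97, so 76 per arm.
- The other two scenarios give 36.6 and 243.4, matching the printed 37 and 243.
- One-sided 0.05: [1.645 × 0.6898 + 0.8416 × 0.6720]² / 0.22² = 59.7, so 60 per arm, or 120 in total, without an interim.

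The printed table is therefore a fixed two-sided calculation.

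**2. The printed boundaries are one-sided.** O'Brien-Fleming-type spending is α(t) = 2 − 2Φ(z_{1−α/2}/√t).

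- One-sided 0.05 at t = 0.66: 2 − 2Φ(1.960/0.8124) = 0.0158, matching the printed 0.016.
- Two-sided 0.05 (0.025 per side) at t = 0.66: 2 × [2 − 2Φ(2.241/0.8124)] = 0.0116 in total, which does not match.

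**3. The final one-sided limit.** Bivariate normal calculation, correlation √t, t from 0.66 to 0.671, one-sided alpha 0.05:

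| Reading | Final one-sided p limit |
|---|---|
| Futility stop at 0.24 binding | 0.048 to 0.049 |
| Futility stop not binding | about 0.045 |
| Alpha increment read as a p limit | 0.034 |

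The printed 0.048 fits the first row. Two-sided 0.05 without an interim adjustment needs one-sided p ≤ 0.025. The three readings differ in the upper end of the zone of conflict, not in whether there is one.

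**4. Example at the final analysis.** 21/76 vs 32/76: the difference is 11/76 = 0.1447 and the pooled rate is 53/152 = 0.3487. The SE is √(0.3487 × 0.6513 × 2/76) = 0.0773, so z = 1.872.

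- One-sided p = 0.031, below all three limits: success.
- Two-sided p = 0.061: failure.
- Continuity-corrected: 0.044 and 0.089. The conflict remains at 0.048 and 0.045, but not at 0.034.

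**5. Operating characteristics.** Exact binomial enumeration, 51 then 76 per arm, control 28%, limits 0.016 (efficacy), 0.24 (futility) and 0.048 (final):

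| Quantity | Uncorrected | Continuity-corrected |
|---|---|---|
| False-positive rate for benefit | 0.050 | 0.032 |
| Power, 28% vs 50% | 86.7% | 82.1% |
| Power if the final limit is 0.034 | 83.9% | 79.3% |

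The final one-sided p falls between 0.025 and 0.048 (uncorrected test) in 1.9% of trials at 28% vs 28%, 9.6% at 28% vs 40%, and 5.0% at 28% vs 50%.

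Monte Carlo error for 10,000 runs at 80% power is ±1.96 × √(0.8 × 0.2/10,000) = ±0.8 points. That does not explain 86.7% or 82.1%, but it does cover 79.3%.

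**The case against.** - **The 1-sided 152 may be right.** A reader might infer that 152 cannot come from a 1-sided design. The documents do not support that. The simulated test is not named, and a corrected test with 0.034 as the final limit gives 79.3%, within simulation error of 80%. That reading treats an alpha increment as a p limit and sits badly with the printed 0.048, but it is not excluded. If power is in fact 82% to 87%, the excess does no harm in itself.
- **0.048 is labelled a futility boundary, not a success limit.** This stands. Taking it as the success limit is an inference. It rests on the recalculation in step 3, on the final look leaving nothing to continue to, and on 7d, which makes the futility stop mandatory.
- **The rest of 7c leans two-sided.** An ordinary chi-squared test is non-directional, and a 95% confidence interval fits two-sided 0.05. That is fair evidence of intent, but it leaves the 1-sided spending in force.
- **The interim paragraph may supersede the earlier text.** Nothing says so, and the two-sided sizing remains.
- **The clash might seem to extend to the interim look, with higher rates of disagreement.** To show that, one must supply two-sided interim limits, and the plan has none. The supported rates are those for the final zone.
- **Interim timing.** Half of the planned 200 is 100, and 100/152 = 0.658, which agrees with 0.66 if no 48-hour outcome is missing. This is a minor clarification, not a second contradiction of weight.

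**Conclusion.** The plan is wrong as written and must be corrected. Two alphas for benefit, 0.025 and 0.05 one-sided, stand side by side for the primary comparison, and nothing in the plan chooses between them. Neither is a slip in one word: removing the two-sided statement leaves the sample-size table without a basis, and removing the 1-sided statement leaves the boundaries without one.

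With limits 0.016/0.24/0.048 the false-positive rate for benefit is 0.050 rather than 0.025. The final result falls in the zone of conflict in 1.9% to 9.6% of trials over the effects examined. These figures assume the uncorrected chi-squared test, a binding futility stop, 51 then 76 evaluable patients per arm and a 28% control rate. If 0.034 is the final limit, the zone is narrower and the doubling does not apply in full.

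That the first specification has no interim look is inferred from its exact match to the fixed-design formula. If it was meant to include the look, its final one-sided limit would fall slightly below 0.025 and the zone would widen. The 1-sided 152 fails to reproduce under the natural reading of the boundaries, but it is not impossible.

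**What to change.** State one governing alpha and sidedness, one final efficacy p threshold and the chi-squared variant (corrected or not), and restate power to match. There are two ways to do this:

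1. **Keep two-sided 0.05.** Replace the boundaries with two-sided group-sequential limits, for example p < 0.0124 at the interim and p < 0.0462 at the final analysis for 102/152. With the futility stop at one-sided 0.24 kept, power at 76 per arm is about 79% uncorrected or 74% corrected.
2. **Keep one-sided 0.05.** Delete the two-sided statement. Label the final success limit: 0.048 if the futility stop is binding, 0.045 if it is not. State the 5% one-sided false-positive rate and, with the 0.048 limit, power of 86.7% uncorrected or 82.1% corrected.

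As a minor clarification, keep one interim timing statement (102 patients with a 48-hour outcome) and delete the one tied to half of enrolment.

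The cost is wording and recalculation, with no extra patients. Option 1 means a slightly lower stated power. Option 2 means openly stating and defending a 5% one-sided error.

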For each arm of the cross-randomization, groups will be compared to identify any imbalance after randomization in relevant characteristics. Comparisons will include factors such as age, race, BMI, comorbidities, surgery type, operative time. Discrete factors will be compared with chi-squared test, and continuous factors will be compared with Mann Whitney U test given prior data suggesting these data will not follow a normal distribution. If data do conform to a normal distribution will utilize t test.

Analysis of the primary efficacy outcome will compare rate of opioid-free rate at 48 hours postoperatively between patients receiving Exparel® plus 0.25% Bupivacaine versus standard 0.25% Bupivacaine alone, using chi-squared test. Logistic regression will be used if adjustment is required for any potential confounders not balanced by randomization, with the treatment effect estimated by the odds ratio and 95% confidence interval. Similar comparison of univariate rates, and adjusted odds ratios will be used for the primary safety endpoints.

All analyses of primary and secondary outcomes will be based on intention to treat (ITT). Per protocol analyses will also be conducted, but treatment success will be based on ITT.

d. Early stopping rules.

The present trial will be stopped prematurely if ANY of the following events occur:

- The trial satisfies futility at interim analysis
- There is a change in the FDA approval status of Exparel®

8. Risks

- a. Medical risks, listing all procedures, their major and minor risks and expected frequency.

Administration of Exparel®/Standard Bupivacaine

1. Major risks:

Date: 12/1/2021

Principal Investigator: [name] [name]

Application Number: IRB00284462

ClinicalTrial.gov Identifier: NCT04826484

- a. CNS toxicity (very rare, ie. tinnitus, confusion)
- a. CNS toxicity (very rare, ie. tinnitus, confusion)
- b. Cardiovascular toxicity (very rare, ie. bradycardia, AV block)
- 2. Minor risks:
 - a. Gastrointestinal discomfort (less than 1% of patients reported in PLAY phase III trial)
 - b. Shortness of breath (less than 1% of patients reported in PLAY phase III trial)
 - c. Constipation (roughly 10% reported in PLAY phase III trial)
 - d. Bruising at injection site (common but short-lived and similar to that of other standard local anesthetics)
- b. Steps taken to minimize the risks.

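### The halt for any LAST episode is tied, on its most natural reading, to the single interim look, so an episode at any other time has a reporting route but no defined enrolment pause

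*Combined protocol and SAP*

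**What the plan says.** Section 7c plans one interim analysis and places the safety review inside it: "At the interim analysis the rates of all-cause surgical complications and those attributable to sequela of the local anesthetics or symptoms related to LAST" were to be evaluated. It then sets a threshold, "An unacceptable rate of all-cause surgical complications was >10" percent. One conditional sentence follows with two triggers: the lower 95% confidence bound for all-cause complications reaching that rate, or, in the words that matter here, "there were any episodes of LAST, the trial would have been halted for further review and consideration of early stopping".

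The timing of the look is given twice. One paragraph says "The interim analysis will be conducted after half" of the patients are enrolled. The next says "One interim analysis of the primary efficacy endpoint will be conducted after information proportion of 0.66 (n = 102"). Planned enrolment is 200: "Assuming a 25% rate of lost-to-follow-up or incomplete follow-up data, we will plan to enroll 100 pediatric patients per arm".

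Section 7d opens "The present trial will be stopped prematurely if ANY of the following events occur" and lists two events, futility at the interim and a change in FDA approval status. It neither mentions LAST nor refers back to 7c.

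Section 8c sends unanticipated problems to the research coordinators and the principal investigator, and calls for a plan of action with IRB communication. It is not limited to any time point and names no pause in enrolment.

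**The concern.** The plan itself treats one LAST episode as enough to halt the trial. If that holds only at the interim look, two situations are left without a defined pause. After an episode in an early patient, the stated rule lets enrolment continue until the look. After an episode in a patient treated later, the stated rule never applies.

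The patients are children aged 6 and over, and LAST complications are a primary safety endpoint in section 7a. Staff who need to know whether to keep enrolling after an episode would look in 7c, 7d and 8c and find no instruction for the time outside the look. What is at stake is a prompt, pre-agreed pause, not the validity of any efficacy result.

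**Working it through.** **Reading the text.** No figure in the plan is in dispute, so the first step is to set the sections side by side.

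| Section | What it provides | When it applies | Enrolment pause defined? |
|---|---|---|---|
| 7c, complication-rate bound | halt for review | interim look | yes |
| 7c, any LAST episode | halt for review | same sentence, same interim text | yes, at the look |
| 7d | mandatory stop for futility or FDA status | interim; any time | not for LAST |
| 8b | monitoring in theatre, at least one hour of recovery observation | every patient | no (care of the individual patient) |
| 8c | reporting, plan of action, IRB communication | any time | no |
| 4h | what follows premature termination | after termination | no (a consequence, not a trigger) |

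A confidence bound is computed at a data look. The LAST trigger shares that sentence and its consequence, in text that opens by naming the interim analysis. No sentence extends it to the rest of accrual.

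**Patients dosed after the look.** Inputs: 200 planned, 25% loss, n = 102 and the half-enrolment timing, all from 7c. Assumptions: enrolled means dosed, allocation is 1:1, and loss up to the look runs at the planned 25%.

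- Look at half of enrolment: 200 − 100 = 100 patients after it (50%), 50 of them on Exparel.
- Look at 102 evaluable patients: 102 / 0.75 = 136 enrolled; 200 − 136 = 64 after it (32%), 32 of them on Exparel.

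The number 102 is best taken as evaluable, because 102 / 152 = 0.67 is close to the stated information proportion of 0.66, and 152 is the evaluable sample size.

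The same arithmetic puts 100 to 136 patients before the look. An episode among them would meet the stated rule only when the look takes place.

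**Can the complication-rate halt stand in?** The smallest number of complications that brings the lower 95% bound to 10% or more is shown below. The plan names neither the interval method nor whether the arms are pooled, so several versions are given.

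| Patients | Exact two-sided | Exact one-sided | Wilson | Wald |
|---|---|---|---|---|
| 50 (one arm) | 10 | 10 | 10 | 11 |
| 68 (one arm) | 13 | 12 | 12 | 14 |
| 100 (both arms) | 17 | 16 | 16 | 18 |
| 136 (both arms) | 22 | 21 | 21 | 23 |

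The bound needs 10 to 14 complications in one arm, or 16 to 23 in both arms together. One LAST episode cannot trigger it under any of these versions.

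**The case against.** The strongest case on the other side has four parts.

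- **A standing trigger is possible.** The LAST condition has no rate, interval or denominator, so it needs no data look to operate, and some readers will take it as applying at all times. That is fair, and it is why the point is put as the most natural reading and not the only one. The text does not settle the matter, and a safety halt should not depend on which reading the site adopts.
- **Section 8c already responds at any time.** This stands. A reader might infer that an episode outside the look would go unanswered; the documents do not support that. The 8c plan of action could well include a pause. The gap is only that none is defined. The protocol also refers to a separate IRB application, which was not available here and may hold further safety-monitoring detail.
- **The omission from 7d proves little.** A reader might infer that 7d contradicts 7c or rules the LAST halt out. It does neither. Section 7d lists events that end the trial, whereas the 7c rule is a halt for review, so leaving it off that list is consistent. Nor is 7d a complete index of 7c: the interim analysis allows "potential early stopping for efficacy or futility", yet 7d lists only futility. What remains is that 7d gives the reader no pointer to the rule in 7c.
- **LAST is rare and the risk is mitigated.** The protocol describes it as exceedingly rare, uses an approved age group, gives 2.5 mg/kg of Exparel against a 4 mg/kg maximum, and observes patients for at least one hour. This stands and limits the weight of the point. The documents give no LAST rate, so no probability of an episode after the look can be derived from them.

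**Conclusion.** The point holds as a minor one. On its most natural reading, 7c's one-episode halt operates at one look only. An episode before or after that look has the 8c response but no defined pause in enrolment. Between 64 and 100 of the planned 200 patients (32 to 50 on Exparel) would be dosed after the look, under the assumptions that enrolled means dosed, loss is 25% and allocation is 1:1. These counts show how much of the trial lies outside the rule once the look has passed; they do not measure expected harm.

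Two further inferences would go too far. Taking 102 as enrolled patients would leave 200 − 102 = 98 after the look, but the information proportion ties 102 to the 152 evaluable patients, so that count is not relied on. Nor does anything here affect type I error, power or the efficacy comparison.

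**What to change.** In 7c, take the LAST trigger out of the complication-rate sentence and state it separately:

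> Any episode of LAST (a clinical diagnosis of LAST by the treating team, not an isolated non-specific symptom), in either arm and at any time during accrual, pauses enrolment pending further review and consideration of early stopping, together with the 8c plan of action and IRB communication.

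The clinical-diagnosis wording matters. Section 7c evaluates LAST-related symptoms but halts on episodes, and section 8a's examples include non-specific signs such as tinnitus and bradycardia. Defining an episode as any one of these could widen the trigger beyond what 7c sets.

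Keep the complication-rate halt at the interim. In 7d, add only a cross-reference to the pause-for-review rules in 7c, placed outside the list of mandatory stops. Inside that list, a pause would read as termination.

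The rule then works the same whichever interim timing is used. The cost is a wording amendment and a possible short accrual pause for a single event, which 7c already accepts at the interim. Sample size and alpha do not change.

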This study will be a single-blinded prospective randomized trial in pediatric patients undergoing minor urologic surgery. Pediatric patients will be randomized in a 1:1 fashion to receive dorsal penile nerve block (circumcision, hypospadias repair, penile cyst excision, meatoplasty, chordeolysis) or spermatic cord block with local wound infiltration (orchiopexy, orchiectomy, inguinal hernia, hydrocelectomy, varicocelectomy) with Exparel® plus 0.25% Bupivacaine versus standard 0.25% Bupivacaine alone. Patient families will also be cross randomized in a 1:1 fashion to receive standard post-operative pain instructions, with or without opioid disposal instructions. Families that consent to participation in the trial will be informed of randomization to Exparel® plus 0.25% Bupivacaine versus standard 0.25% Bupivacaine but will be blinded to arm assignment. Families will also be informed that they will be receiving postoperative pain instructions, however they will not be informed of whether or not they receive opioid disposal instructions.

No other standard pre-, peri- or post-operative pediatric urologic surgery procedures will be affected. Routine care includes an initial clinic consultation, physical examination, and informed consent prior to proceeding with surgery. Informed consent for participation in the study may also be obtained in the preoperative area during the day of surgery. Eligibility will be confirmed at the time of consent. Patient will be randomized after consent is obtained and appropriate postoperative pain instructions with or without opioid disposal instructions will be given at that time to minimize drop out.

Anesthesia team will be notified when local wound infiltration or penile nerve block is being performed as is standard operating procedure, however we will not dictate what other intra or peri-operative analgesia is given. All blocks will be performed by the surgical team using landmark techniques.

Patients will be given the option of returning to the Johns Hopkins clinic or local follow-up (with a provider) for wound check approximately 7-14 days after surgery.

[figure not shown]

Figure 1. Diagram of plan for stratified randomization of patients to arms and outcomes assessed.

Date: 12/1/2021

Principal Investigator: [name] [name]

Application Number: IRB00284462

ClinicalTrial.gov Identifier: NCT04826484

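### Adjustment of the primary comparison depends on imbalance tests that include operative time, a post-randomisation variable, and the plan does not say whether the crude or the adjusted result decides success

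*Combined protocol and SAP*

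**What the plan says.** All of the analysis wording is in section 7c, under Statistical Analysis.

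- **Screen.** The "groups will be compared to identify any imbalance after randomization in relevant characteristics". The tools are hypothesis tests: "Discrete factors will be compared with chi-squared test, and continuous factors will be compared with Mann Whitney U test", with a t test if the data look normal. No significance level is given for the screen.
- **Factors screened.** "Comparisons will include factors such as age, race, BMI, comorbidities, surgery type, operative time". The list is open-ended.
- **Primary comparison.** "Analysis of the primary efficacy outcome will compare rate of opioid-free rate at 48 hours postoperatively", by chi-squared test and without any condition attached.
- **Conditional model.** "Logistic regression will be used if adjustment is required for any potential confounders not balanced by randomization". The arm comparison would then be reported as an odds ratio with its 95% interval.
- **Safety.** "Similar comparison of univariate rates, and adjusted odds ratios will be used for the primary safety endpoints".

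The plan ties treatment success to the intention-to-treat analysis. That settles the population, not whether the crude or the adjusted result counts.

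On timing, section 4a says: "Patient will be randomized after consent is obtained". Surgery follows.

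**The concern.** Under sound randomisation, differences between arms in factors fixed beforehand are due to chance. Testing for them and letting the result choose the model makes the model depend on the data. The plan gives no threshold, no fixed covariate set and no order of precedence, so a crude comparison and an adjusted odds ratio could both be put forward as the answer. The two odds ratios are not interchangeable even without bias, because an odds ratio changes meaning when prognostic covariates are added.

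Operative time is a different matter. It is measured after allocation, so the arm can influence it. If it does, the screen will tend to pick it out for that very reason. The model would then condition on a consequence of treatment, and the adjusted odds ratio would no longer estimate the effect of assignment.

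**Working it through.** **1. Reproduce the plan's figure.** Section 7c gives 28% against 50%, 80% power, two-sided alpha 0.05 and 76 per arm. The pooled-variance formula without continuity correction, with mean rate 0.39, is

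n = [1.960 × √(2 × 0.39 × 0.61) + 0.842 × √(0.28 × 0.72 + 0.50 × 0.50)]² / 0.22² = (1.352 + 0.566)² / 0.0484 ≈ 76.

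The stated size is therefore that of an unadjusted two-proportion test.

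**2. Chance that something is flagged by luck.** Assume independent tests at 0.05 (the level is my assumption). The chance is 1 − 0.95⁶ = 26.5% for the six named factors. For the five other than operative time it is 1 − 0.95⁵ = 22.6%. For ten factors it is 1 − 0.95¹⁰ = 40.1%. This is how often a model would be triggered, not an error rate.

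**3. Can the arm affect operative time?** Randomisation comes after consent and before surgery (section 4a). The surgeon learns the arm in the operating room when the block is ready (section 4d). The intervention arm then receives two agents in sequence (section 6a). A difference is possible, but the documents give no figure for it.

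**4. Simulate the rule.** The rule is: screen at 0.05, fit a logistic model with the flagged factors, otherwise use chi-squared. Fixed inputs are 76 per arm, 28% opioid-free and no total drug effect. The shift is how much longer operative time is in the Exparel arm. The shifts and prognostic strengths are all assumptions.

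- Structure A: operative time itself lowers the chance of being opioid-free (log OR −0.6 per SD); five baseline factors are prognostic at 0.4 per SD; 6,000 trials.
- Structure B: operative time correlates 0.7 with case severity, and severity lowers the chance; 1,500 trials (0.1-0.2 SD) or 4,000 trials.
- Structure C: operative time has no effect of its own but shares an unmeasured cause with the outcome (correlation 0.5 with time, log OR +1.0 on being opioid-free); 6,000 trials.

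| Structure | Shift (SD) | Type I error of the rule | Median OR (null value 1) |
|---|---|---|---|
| A | 0 | 4.5% | 1.00 |
| B, severity log OR 0.3-1.0 in size | 0.1-0.2 | 4.6-6.5% | 1.00-1.07 |
| B | 0.3 | about 6% | – |
| B, severity log OR −0.6 | 0.5 | 7.6% | 1.22 |
| B, severity log OR −1.0 | 0.5 | 11.5% | 1.39 |
| A | 0.5 | 9.0% | 1.28 |
| C | 0.5 | 7.4% | 0.83 |

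In the A and C rows the OR is the rule's median over all trials. The 1.39 is the median among trials where operative time was flagged. Taking the better of the two p-values gives 5.2% (A, no shift), 11.2% (A, 0.5 SD) and 9.5% (C). At a 0.5 SD shift operative time is flagged in about 84-85% of trials. Repeat runs of B put type I error at about 11-12% (log OR −1.0) and 7% (−0.6) at 0.5 SD, and at 4-6% for 0.1-0.3 SD. Simulation error explains the 6.5%: with 1,500 trials the standard error is √(0.05 × 0.95 / 1,500) = 0.6 percentage points.

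**5. When the drug works (28% against 50%).** The crude OR is (0.50/0.50) / (0.28/0.72) = 2.57; the simulated median is 2.59. In A the rule's median is 2.61 with no shift, 2.88 at 0.25 SD and 3.49 at 0.5 SD. In C at 0.5 SD it is 2.25, and power falls to 61.5%.

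**6. Comparator.** In every A and C scenario the plain chi-squared test kept type I error at 4.8-4.9% and power at 80-81%.

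The simulations ignore the interim analysis.

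**The case against.** The strongest reply is that the plan does name a primary test. The chi-squared comparison is unconditional, the sample size is built on it, and logistic regression reads as a follow-on. This stands in large part: one sentence saying that chi-squared decides would remove most of the concern. That sentence is missing.

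Second, operative time is listed for comparison, not named as a covariate, and the plan does not say that a flagged factor enters the model automatically. That is true. But nothing excludes it, and the model is offered for whatever is not balanced.

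Third, any shift may be small. Both arms receive a block, operating done before the block is blind to arm, and the arms differ by one additional injection. This limits the shift and makes 0.5 SD an upper illustration rather than an expectation. It does not rule a shift out, because the two agents are given in sequence and the surgeon knows the arm from the block onward.

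A reader might also infer that leaving out surgery type and age when they happen to be balanced throws away substantial precision. The documents do not show this. The background links age to the quantity of opioid prescribed, not to being opioid-free, and gives no such figure for surgery type. The caption of Figure 1 mentions stratified randomisation, but the figure is not in the text available here, so the strata cannot be taken into account.

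**Conclusion.** The point holds as a defect in the analysis rule, with a conditional size. What is certain from the text is that the model is chosen after looking at the data, that operative time is among the screened factors, and that no order of precedence is given. If the arm does not affect operative time, type I error stays at about 4.5-5%, and the harm is confined to an unfixed model and two possible headline estimates. If it does and operative time is selected, bias can go either way: type I error is about 4-6% at shifts of 0.1-0.3 SD and about 7-12% at 0.5 SD. At 0.5 SD the median adjusted OR is roughly 1.2-1.4, or about 0.8 under the shared-cause structure. Those sizes rest on assumed shifts and prognostic strengths.

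Two stronger readings are not supported. A reader might infer that the trial's type I error is 12%; that needs a 0.5 SD shift and a strong severity effect, neither of which is in the documents. A reader might also infer that the primary test itself is data-dependent; the chi-squared test is prespecified and holds its level. The fault lies in the conditional model and its unstated standing.

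**What to change.** In section 7c, under Statistical Analysis:

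1. Name one deciding analysis for the 48-hour opioid-free rate. Either state that the chi-squared test alone decides success, or specify one model whose covariates are fixed before randomisation (any stratification factors, surgery/block type, age) and fit it whatever balance is observed. Label the other as supportive.
2. Keep the between-arm table as description and delete imbalance testing as a trigger for adjustment.
3. Exclude operative time from any adjustment set and report it by arm descriptively.
4. Apply the same rule to the primary safety endpoints.

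Keeping chi-squared as decisive costs a few sentences and leaves 76 per arm unchanged. Choosing the model makes the headline estimate model-based, and the interim boundaries must then be applied to that test.
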